Note: In patients with LV thrombus complicated with hemorrhagic stroke \geq 4 weeks or recent ischemic stroke/transient ischemic attack, the investigators decided whether anticoagulation therapy can be given according to the specific situation.

Study treatments

The enrolled patients were assigned to a standard dose of rivaroxaban 20 mg qd (it can be reduced to 10-15 mg qd depending on the patient's condition and renal function) after the confirmation of LV thrombus by contrast-enhanced echocardiography.

Study endpoints

The primary endpoint of this study was the LV thrombus resolution rate at 12 weeks confirmed on contrast-enhanced echocardiography.

The secondary endpoint events:

- 1) the LV thrombus resolution rate at 6 weeks, the LV thrombus resolution or reducing rate at 6 weeks, the LV thrombus unchanging or increasing rate at 6 weeks, the LV thrombus resolution or reducing rate at 12 weeks, and the LV thrombus unchanging or increasing rate at 12 weeks. (disappearance of thrombus as an indicator of resolution rate, $>15\%$ reduction in thrombus length or thickness measured by ultrasonography as an indicator of reduction rate, $\leq 15\%$ variation in length or thickness as an indicator of unchanged rate, and $>15\%$ increase in length or thickness as an indicator of increasing rate)
- 2) incidence of the composite of stroke, systemic embolism, myocardial infarction, and cardiovascular death during follow-up
- 3) major bleeding according to the International Society on Thrombosis and Haemostasis [ISTH] criteria and clinically related non-major hemorrhage events during follow-up.

An adverse event was any adverse medical event, including an exacerbation of a pre-existing condition or abnormal laboratory findings on clinical examination of a subject on medication, which was not necessarily related to such treatment. A serious adverse event can be fatal, life-threatening, requiring hospitalization or prolongation of an ongoing hospital stay, resulting in persistent or significant disability/incapacity, and it was any adverse medical event that represents a significant risk of congenital

anomalies/birth defects and/or other clinically significant serious events.

Study procedures

First of all, for patients with LV thrombus (regardless of the type of fundamental disease) confirmed by surface ultrasound within three months, who met the inclusion criteria and did not meet the exclusion criteria, informed consent was signed. Blood routine, biochemical and coagulation tests were required to complete, and baseline contrast-enhanced echocardiography was evaluated. Secondly, a standard dose of rivaroxaban 20 mg qd (it can be reduced to 10-15 mg qd depending on the patient's condition and renal function) was administered to the enrolled patients. Then, at 6 and 12 weeks, hematological parameters such as routine blood tests, liver and kidney function, coagulation, and other hematological parameters were re-examined. At the same time, contrast-enhanced echocardiography was also performed and thrombus size, anticoagulant use, and endpoint events were documented as well. After 12 weeks, the investigator decided on the follow-up treatment plan according to the patient's condition. Clinic or telephone follow-up visits were conducted at 6 months to collect events and anticoagulant use. During the entire study, patients were educated about anticoagulation and bleeding observation, informed about the importance of maintaining treatment compliance and notified about the management of bleeding in the presence of bleeding according to the EHRA 2018 NOACs clinical guidelines.

Statistics Analysis Plan

Patients who received at least one dose of rivaroxaban were included in the safety set population. Patients who completed treatment and follow-up visits were included in the primary analysis set which was used for evaluating efficacy outcomes.

Normally distributed continuous data were presented as mean and standard deviation (SD) while non-normally distributed continuous data by the median and interquartile range (IQR), and the dichotomous data were computed using frequency and percentage. The rates and their 95% confidence intervals (CIs) were calculated for the primary endpoint and the secondary endpoints. The hazard ratio (HR) was estimated with or without adjustment for covariates using Cox regression models. Significant variables in the univariate analysis and other variables of interest were included in the subgroups to investigate the potential influences on the resolution of the thrombus, where continuous variables were dichotomized based on the median value. A forest plot was created to display subgroup analysis. To test for changes in diffusion data across different time points of thrombus resolved vs. thrombus unresolved (including reduced, unchanged, and enlarged thrombus), linear mixed models were tested using the *lme* function in R. To investigate any significant interactions in more detail, we then ran corresponding pairwise comparisons using the *emmeans* function in R. Comparisons were regarded as two-sided, and statistical significance was determined by the P value of 0.05. All analyses were scheduled for completion with R version 3.5.1 (The R Project for Statistical Computing, Vienna, Austria).

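### The 6-month bleeding and embolic rates pool time on rivaroxaban with investigator-chosen treatment after week 12, so they cannot be attributed to rivaroxaban alone.

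*Combined protocol and SAP*

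**What the plan says.** The title gives the subject of the study as the effectiveness and safety of rivaroxaban. Study design makes it a single-arm observational study.

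- **Treatment.** Study treatments: "The enrolled patients were assigned to a standard dose of rivaroxaban 20 mg qd", with reduction allowed. No duration is stated there or in Study procedures.
- **After week 12.** Study procedures: "After 12 weeks, the investigator decided on the follow-up treatment plan".
- **Event endpoints.** Study endpoints, secondary endpoint 2: "incidence of the composite of stroke, systemic embolism, myocardial infarction, and cardiovascular death during follow-up". Secondary endpoint 3 covers ISTH major bleeding and "clinically related non-major hemorrhage events during follow-up". Neither has an end date. Every thrombus endpoint, by contrast, is fixed at week 6 or week 12.
- **Data collected.** At weeks 6 and 12, "thrombus size, anticoagulant use, and endpoint events were documented as well". Later, "Clinic or telephone follow-up visits were conducted at 6 months to collect events and anticoagulant use".
- **Analysis.** Statistics Analysis Plan: "Patients who received at least one dose of rivaroxaban were included in the safety set population". Rates with 95% confidence intervals are planned for the primary and secondary endpoints. There is no on-treatment window, no censoring at stop or switch, no person-time denominator and no separate week-12 event rate. The Cox models it mentions have no stated event outcome or exposure term.

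**The concern.** A reader of a study on the safety of rivaroxaban will take its 6-month bleeding figure as the figure for the drug. Under this plan, that figure can contain time on rivaroxaban, time on another anticoagulant and time on none, in proportions settled by clinical decisions after week 12. Those decisions follow the patient's condition, so patients who stop, switch or continue may also differ in risk. No control group passes through the same mix.

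The bleeding and embolic results are at stake. Bleeding is the only safety outcome named as an endpoint. The two results may be distorted in opposite directions: time off drug could lower the bleeding rate per unit time and raise the embolic rate. The primary endpoint, thrombus resolution at week 12, is not affected.

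**Working it through.** The documents give no expected event rate, event count or sample size, so there is no figure of the plan's own to reproduce. The check is an exposure-time calculation.

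**Inputs from the documents:** the investigator decides treatment after week 12; last event collection is at 6 months, taken as 26 weeks. **Assumptions (not in the documents):** *f*, the share continuing rivaroxaban after week 12; *k*, the off-drug hazard divided by the on-drug hazard; hazards constant within each state; no stopping before week 12.

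**Step 1. Share of the window.** Before the decision point: 12/26 = 46%. Discretionary: 14/26 = 54%.

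**Step 2. Share of person-time on rivaroxaban** = (12 + 14*f*)/26. All continue: 26/26 = 1.00. Half continue: 19/26 = 0.73. None continue: 12/26 = 0.46.

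**Step 3. Average 6-month rate per unit time, relative to the on-drug rate** = (12 + 14[*f* + (1 − *f*)*k*])/26.

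For *f* = 0.5 and *k* = 0.2: (12 + 14 × 0.6)/26 = 20.4/26 = 0.785. The same formula gives:

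| Share continuing | Bleeding, k = 0.2 | Bleeding, k = 0.5 | Embolic, k = 2 | Embolic, k = 3 |
|---|---|---|---|---|
| 100% | 1.00 | 1.00 | 1.00 | 1.00 |
| 90% | 0.957 | 0.973 | 1.054 | 1.108 |
| 50% | 0.785 | 0.865 | 1.269 | 1.538 |
| 30% | 0.698 | 0.812 | 1.377 | 1.754 |
| 0% | 0.569 | 0.731 | 1.538 | 2.077 |

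The range runs from no distortion to about 43% too low for bleeding and about twofold too high for embolic events. The formula has only an on-drug and an off-drug state. Patients who switch to another anticoagulant would need their own *k*, and if those who stop are mainly at low risk, the embolic *k* could be below 1.

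**Step 4. The same inputs as a simple percentage of patients.** With *f* = 0.5 and *k* = 0.2, the average cumulative hazard to week 26 is 20.4 on-drug-week equivalents, against 12 at week 12: 20.4/12 = 1.7 times as large. As an illustration, assume a 12-week bleeding risk of 5%:

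- 6-month risk for those continuing: 1 − 0.95^(26/12) = 10.5%.
- 6-month risk for those stopping: 1 − 0.95^(14.8/12) = 6.1%, where 14.8 = 12 + 14 × 0.2.
- Pooled, half and half: 8.3%.

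The pooled percentage is above the week-12 value of 5% and below the 10.5% expected if everyone had stayed on drug. With complete follow-up and a fixed denominator, it can only stay level or rise after week 12. The shortfall in Step 3 therefore applies to a rate per unit time, or to a comparison with 26 weeks of continuous treatment.

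**The case against.** The strongest reply is that events after starting rivaroxaban, with later treatment left to the investigator, are a legitimate treatment-policy description in an exploratory observational study. That stands. The plan does not name this as its target, however, and the figure needs that label if it is not to be read as a property of the drug.

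Four stronger readings are tempting, and the documents do not support them:

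- **That rivaroxaban ends at week 12.** No duration is stated. Week 12 is a decision point, and patients may continue.
- **That the plan fixes a 6-month window and attributes every event to rivaroxaban.** The end of follow-up is undefined; 6 months is only the natural reading. There is no attribution rule, and the adverse event definition in Study endpoints says that events need not be related to treatment.
- **That the event rates do not measure the safety of rivaroxaban.** The first 12 weeks inform on it directly, and endpoint events are documented at weeks 6 and 12.
- **That the reported bleeding rate will be 20% to 30% too low.** Those figures rest on assumed inputs and on a rate per unit time. The Statistics Analysis Plan summarises dichotomous data by frequency and percentage and specifies no person-time, so a simple percentage is the likelier output. A 12-week percentage would be equal to or lower than the 6-month one, so it could look more favourable, and it leaves out bleeds on rivaroxaban after week 12.

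These points limit the claim. They do not supply the missing link between events and exposure: that some patients may continue does not help when the plan never separates them from those who stop or switch.

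**Conclusion.** The concern holds in a limited form. On the natural reading, 54% of the event window is discretionary treatment, and nothing in the analysis plan separates it from the first 12 weeks. In this single-arm study, the pooled 6-month bleeding and embolic rates cannot be attributed to rivaroxaban alone.

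Neither the size nor the direction of the distortion can be fixed from the documents, because the share stopping or switching and the off-drug hazards are not given. The Step 3 ratios are illustrations under constant hazards and two treatment states. The endpoints are secondary and the study is exploratory, but the repair is cheap and makes the safety result interpretable, so it should be made.

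**What to change.** In the Statistics Analysis Plan:

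1. Define the end of follow-up for the bleeding endpoint and the embolic composite.
2. Report bleeding (safety set) and the composite, each with a 95% confidence interval, separately from first dose to week 12 and from first dose to 6 months.
3. Label the 6-month figures as rivaroxaban followed by investigator-chosen treatment.
4. Add, as a supportive analysis, an on-treatment rate per person-time from first to last rivaroxaban dose plus a fixed lag set in advance. Use the recorded anticoagulant use, and capture stop and switch dates where available.

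**Cost.** Items 1 to 3 need SAP wording and one extra table, using events already documented at week 12 and 6 months. Item 4 depends on stop and switch dates, which Study procedures does not explicitly require. The 12-week window will hold fewer events and give wider intervals. No change to treatment is proposed.

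### The efficacy set holds only completers and there is no rule for missing scans or deaths, so the 12-week resolution rate is open to selection bias, probably upward.

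*Combined protocol and SAP*

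**What the plan says.** The Study endpoints section sets the primary outcome: "The primary endpoint of this study was the LV thrombus resolution rate at 12 weeks confirmed on contrast-enhanced echocardiography".

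The Statistics Analysis Plan then defines two populations. The dosed population is named for safety only: "Patients who received at least one dose of rivaroxaban were included in the safety set population". Efficacy has a narrower set: "Patients who completed treatment and follow-up visits were included in the primary analysis set which was used for evaluating efficacy outcomes".

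For the primary rate itself, the only analysis instruction is: "The rates and their 95% confidence intervals (CIs) were calculated for the primary endpoint and the secondary endpoints". The plan also lists Cox and linear mixed models, but neither changes the denominator of this proportion. Nothing in the document says how to count a death before week 12, an early stop, a loss to follow-up, or a missing or unreadable 12-week scan.

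Two statements under Study procedures affect what completion means. On treatment: "After 12 weeks, the investigator decided on the follow-up treatment plan". On later contact: "Clinic or telephone follow-up visits were conducted at 6 months to collect events and anticoagulant use".

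Secondary endpoint 2 is the "incidence of the composite of stroke, systemic embolism, myocardial infarction, and cardiovascular death during follow-up". The SAP does not say in which set it is analysed.

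**The concern.** Membership of the efficacy set is settled after the first dose, by events that can be related to the outcome. A patient who dies before week 12 cannot have confirmed resolution, yet is removed from the denominator. Some exclusions act the other way: a patient who stops because the thrombus had gone by week 6 is a success that is lost.

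The set is also ambiguous. If the 6-month contact is a required visit, a patient with a valid 12-week scan can be dropped from a 12-week endpoint because of something that happened later. Two analysts could report different denominators from the same data.

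The study has one arm, so no comparator shares the selection, and the reported rate is itself the result. The study is exploratory and has no success threshold. What is at stake is a misleading estimate and confidence interval, not a false pass or fail. If the composite were also analysed in completers, the cardiovascular deaths it is meant to count could drop out.

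**Working it through.** **Inputs.** The documents give no sample size, dropout or expected resolution rate, so there is no planned figure to reproduce. Every number below is an assumption chosen to show scale.

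**Formula.** Let p be the resolution rate in completers, q the rate in excluded patients and d the share excluded.

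- All-treated rate = (1 - d) × p + d × q
- Error of the completer rate = p - all-treated rate = d × (p - q)

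The sign depends on q, which the plan leaves unobserved or unused.

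**Range at p = 80%.** Each cell gives the all-treated rate and, in brackets, the error of the completer rate in percentage points.

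| Excluded (d) | q = 0% | q = 25% | q = 50% | q = 80% | q = 100% |
|---|---|---|---|---|---|
| 5% | 76 (+4) | 77.25 (+2.75) | 78.5 (+1.5) | 80 (0) | 81 (-1) |
| 10% | 72 (+8) | 74.5 (+5.5) | 77 (+3) | 80 (0) | 82 (-2) |
| 20% | 64 (+16) | 69 (+11) | 74 (+6) | 80 (0) | 84 (-4) |

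For example, with d = 10% and q = 25%: 0.9 × 80 + 0.1 × 25 = 74.5.

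**Asymmetry.** The largest upward error is d × p (q = 0) and the largest downward error is d × (1 - p) (q = 1). Their ratio is p / (1 - p): 2.3 at 70%, 4 at 80% and 9 at 90%.

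**Worked example, with Wilson 95% intervals.** Suppose 60 patients are treated, 54 complete and 43 of these resolve. Of the 6 excluded, 2 died before week 12, 2 have a 12-week scan showing resolution and 2 have no scan.

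| Rule | Resolved / denominator | Rate (95% CI) |
|---|---|---|
| Completers, as planned | 43/54 | 79.6% (67.1-88.2) |
| All treated; deaths and missing scans not resolved | (43 + 2)/60 = 45/60 | 75.0% (62.8-84.2) |
| All treated; missing scans in survivors resolved | (45 + 2)/60 = 47/60 | 78.3% (66.4-86.9) |
| Extreme: none of the 6 resolved | 43/60 | 71.7% (59.2-81.5) |
| Extreme: all 6 resolved | 49/60 | 81.7% (70.1-89.4) |

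In this example even the best case that respects the two deaths, 78.3%, is below the completer rate.

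**Composite endpoint.** This is a separate illustration and applies only if the composite is analysed in completers. Suppose there are 3 cardiovascular deaths and 2 patients with non-fatal events among 60 treated. The incidence is 5/60 = 8.3% (3.6-18.1). Removing only the 3 patients who died gives 2/57 = 3.5% (1.0-11.9).

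**The case against.** The best case for the plan is that neither the direction nor the size of the bias comes from the documents. The ratio p / (1 - p) compares extremes, not likelihoods, and it favours upward error only when p is above 50%: it is 1 at 50% and 0.67 at 40%. With few exclusions the effect is small: at 5% excluded and p = 80% the error runs from +4 to -1 points. In the 60-patient example the shift from 79.6% to 75.0% lies well inside the sampling error. The study is descriptive and tests no threshold. Treatment passes to the investigator only after week 12, so the natural reading is that study treatment ends there. Finally, counting missing scans as unresolved is deliberately pessimistic.

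Much of this limits the claim without removing it. The size is unknown, and upward is an inference. That inference rests mainly on early deaths, which are non-successes whatever p is. Sampling error is no defence, because the interval does not cover selection and would be centred on the wrong quantity. The 12-week reading of treatment is reasonable, but the 6-month contact is itself called a follow-up visit, so the ambiguity over required visits remains. The harm to the composite is conditional on a set that the SAP does not name.

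The choice of headline for missing scans is open to debate. One could leave survivors without a scan out of the denominator and show bounds beside that rate; in the example, if all completers were scanned, this gives 45/(60 - 2) = 45/58 = 77.6%. That choice does not affect the case for changing the denominator, using all available scans and reporting exclusions.

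**Conclusion.** The concern holds. The stated rule conditions the primary rate of a single-arm study on events after the first dose, and nothing else in the plan offsets it. This is a rule that biases the estimate if followed, not merely a missing detail. The bias is probably upward. Assuming 80% resolution in completers, the error is +8 to -2 points with 10% excluded and +16 to -4 with 20% excluded; with nobody excluded there is none, but the plan neither ensures nor reports that. Confidence is high on the completer restriction and the missing rule, and lower on direction and size. Because it determines the denominator of the primary endpoint, it must be fixed, even in an exploratory study.

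**What to change.** Amend the Statistics Analysis Plan as follows.

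- **Primary efficacy denominator:** all patients with thrombus confirmed at baseline who took at least one dose of rivaroxaban.
- **Scans:** use every available 12-week contrast echocardiogram, whatever the treatment status and whether or not the 6-month contact took place.
- **Deaths and missing scans:** count a death before week 12 as not resolved. Count a missing scan as not resolved in the primary rate and label that rate a conservative lower bound. Report beside it the best case, with missing scans in survivors counted as resolved.
- **Completer rate:** keep it as a sensitivity analysis, name the visits that completion requires, and report the number excluded by reason.
- **Composite of stroke, systemic embolism, myocardial infarction and cardiovascular death:** state that it is analysed in the existing safety set from first dose.

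The SAP should also say where deaths and missing scans fall in the secondary 6- and 12-week response categories, so that they do not enter one category by default.

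The cost is wording only, with no added visits or scans. The protocol does not say that patients who stop rivaroxaban are still scanned at week 12, so any without a scan are handled as missing. The headline rate may be a few points lower, and it is conservative where scans are missing.

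### Bleeding over follow-up has no censoring rule or absolute time-to-event estimate; a crude percentage of the one-dose safety set can only understate 6-month bleeding risk

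*Combined protocol and SAP*

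**What the plan says.** All references are to the combined protocol and SAP.

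- **Endpoints.** Under Study endpoints, secondary endpoint 2 is the "incidence of the composite of stroke, systemic embolism, myocardial infarction, and cardiovascular death during follow-up". Secondary endpoint 3 is ISTH major bleeding and "clinically related non-major hemorrhage events during follow-up". Both accrue over time, unlike the scan endpoints at 6 and 12 weeks.
- **Observation.** Study procedures schedules visits at 6 and 12 weeks, and then: "Clinic or telephone follow-up visits were conducted at 6 months to collect events and anticoagulant use".
- **Analysis sets.** The Statistics Analysis Plan says: "Patients who received at least one dose of rivaroxaban were included in the safety set population". It also says: "Patients who completed treatment and follow-up visits were included in the primary analysis set which was used for evaluating efficacy outcomes". It does not assign the bleeding endpoint or the composite to either set by name.
- **Summary measures.** In the same section, "the dichotomous data were computed using frequency and percentage", and "The rates and their 95% confidence intervals (CIs) were calculated for the primary endpoint and the secondary endpoints".
- **Time-to-event methods.** The only one is this: "The hazard ratio (HR) was estimated with or without adjustment for covariates using Cox regression models". Its outcome, time origin and censoring are not given, and the sentence after it concerns thrombus resolution.

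The plan has no cumulative-incidence or Kaplan-Meier estimate, no person-time denominator, no fixed horizon for the event endpoints, and no rule for patients lost to follow-up.

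**The concern.** A percentage is a sound estimate of risk when everyone in the denominator has been observed for the whole period. For a scan at a fixed visit that is simply a matter of who was scanned. For bleeding up to 6 months in a set with no minimum observation time, it depends on nobody being lost. A patient who stops attending in week 2 and cannot be reached at 6 months adds one to the denominator for the full period, but can add to the numerator only during the first two weeks.

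The study title puts safety beside effectiveness. With a single arm there is no comparator that would share the error, so the absolute bleeding risk is itself the safety result. The Cox model does not help, since it yields a hazard ratio and not an absolute risk.

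**Working it through.** The plan states no sample size, event rate or dropout rate, so it offers no figure to reproduce. The check has three parts.

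**1. Which reading of the plan is natural?** The word for rate is applied in one sentence to the primary endpoint, a 12-week resolution proportion, and to the secondary endpoints. The sentence before it prescribes percentages for dichotomous data, and person-time appears nowhere. The safety set has no other stated use, so bleeding as a percentage of that set is the natural reading, though the plan does not spell it out.

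**2. Bleeding in the safety set.**

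*Direction.* The denominator is fixed at all treated patients. The patients with an observed bleed are a subset of those who would be seen to bleed with complete follow-up. The crude percentage therefore cannot exceed the full-follow-up value. No assumption about why patients are lost is needed for this.

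*Size.* This needs assumptions: true 6-month risk p, constant hazard λ = −ln(1 − p) with 6 months as one unit of time, and a fraction d lost independently of risk. Let q be the chance of a bleed before loss in a lost patient. Then

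- crude percentage = (1 − d)p + dq
- relative understatement = d(1 − q/p)
- loss after a few doses (2% of follow-up, about 4 days): q = 1 − exp(−0.02λ)
- loss uniform over follow-up: q = 1 − (1 − exp(−λ))/λ

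For p = 10%, λ = 0.1054. Early loss gives q = 0.0021, so the understatement is 0.98d. Uniform loss gives q = 0.0509, so it is 0.49d. For example, with d = 20% and early loss: 0.80 × 0.10 + 0.20 × 0.0021 = 0.0804.

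| Lost (d) | Crude %, early loss | Relative shortfall | Crude %, uniform loss | Relative shortfall |
|---|---|---|---|---|
| 5% | 9.51 | 5% | 9.75 | 2% |
| 10% | 9.02 | 10% | 9.51 | 5% |
| 20% | 8.04 | 20% | 9.02 | 10% |
| 30% | 7.06 | 29% | 8.53 | 15% |

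The relative shortfalls are the same, to the nearest percent, for p = 3%, 5% and 15%.

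A different loss pattern gives similar answers. With loss at week 2 of 26, q = 1 − exp(−2λ/26) = 0.0081, and the crude value is 9.1%, 8.2% and 7.2% for d = 10%, 20% and 30%. With a constant dropout hazard μ = −ln(1 − d), the crude value is λ/(λ + μ) × [1 − exp(−(λ + μ))], which gives 9.5%, 9.0% and 8.4%.

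**3. The composite.** If it is analysed in the safety set, part 2 applies unchanged. If it counts as an efficacy outcome, it is analysed in completers. A lost patient is then removed from numerator and denominator alike, and under non-informative loss 10% stays 10%. The difficulty there is that a patient who dies may not count as a completer, although cardiovascular death is a component. If a share f of composite events is fatal and every such patient is excluded, the result is p(1 − f)/(1 − pf). For p = 10%, f = 30% gives 0.07/0.97 = 7.2%, and f = 50% gives 0.05/0.95 = 5.3%. The values of f are assumptions too.

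**The case against.** The strongest reply is that this is a small, descriptive matter. The study is exploratory, single-centre and single-arm, with short follow-up on the same schedule for everyone. Counts and percentages with the number lost would be a reasonable summary. Nothing in the documents suggests 30% loss; with 5% uniform loss, 10% becomes 9.75%. If 50 to 100 patients were enrolled (an assumption), a 95% CI around 10% is roughly ±8 to ±6 points, since 1.96 × √(0.09/50) = 0.083 and 1.96 × √(0.09/100) = 0.059. That is far wider than the shift from modest loss. This stands as a limit on importance, but it does not remove a bias of known direction that is cheap to avoid.

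Three stronger readings are tempting and are not supported.

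- *A reader might infer that the plan instructs lost patients to be counted as event-free.* It does not. That follows from a percentage of the one-dose set. Events per person-time is not ruled out, though nothing points to it, and the plan would have to say so.
- *A reader might infer that strokes and the rest of the composite are understated by the same route.* That holds only if the composite uses the safety set, which is not stated.
- *A reader might infer that treating death from another cause as a non-event is a mistake.* It is not. A competing-risks cumulative incidence also never counts such a patient as having the event. The fault lies in unobserved time, not in the handling of death.

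**Conclusion.** The point holds for bleeding, on the natural but unstated reading that it is reported as a percentage of all patients with one dose. On that reading 6-month bleeding risk can be understated but not overstated. The direction needs no assumption about the reasons for loss. The size does: with constant hazard and loss unrelated to risk, the relative understatement is about half the dropout fraction when loss is spread over follow-up (2% to 15% for assumed dropout of 5% to 30%), and nearly the full fraction when loss is early (5% to 29%). It would be larger if patients who bleed are likelier to be lost, and is negligible if few are lost. Since the documents give neither a dropout nor an event rate, no particular size can be attributed to this trial.

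For the composite the conclusion is conditional: the same mechanism in the safety set, or exclusion of non-completers, possibly including cardiovascular deaths, in the completer set. This is a worthwhile correction to the analysis of secondary endpoints 2 and 3. It does not affect the primary endpoint.

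**What to change.** In the Statistics Analysis Plan:

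1. State that secondary endpoints 2 and 3 are analysed in all patients who received at least one dose.
2. Report the cumulative incidence of the first event from first dose by the Aalen-Johansen estimator, censored at last contact. Treat any death that is not itself an endpoint event as a competing event.
3. Give the estimate with its 95% CI and number at risk at 12 weeks and at 6 months. The 12-week figure matters because, under Study procedures, treatment after that point is individually decided.
4. Show raw event counts and the number and timing of losses alongside. The estimator assumes that loss is unrelated to risk, and readers need these figures to judge that.
5. Keep plain proportions for the scan endpoints.

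The cost is a few sentences and a few lines of R, plus event dates and last-contact dates on the case report form. Reported risks may become slightly less favourable. With complete follow-up the estimate equals the crude proportion, so nothing is lost if retention turns out to be good.

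### Should hazard ratios for thrombus resolution come from a grouped-time model instead of Cox, since resolution is seen only at the week-6 and week-12 scans?

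*Combined protocol and SAP*

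**What the plan says.** The sentence at issue, in the Statistics Analysis Plan, is "The hazard ratio (HR) was estimated with or without adjustment for covariates using Cox regression models". It names no outcome, time origin, event-time rule or tie method. The next sentence takes significant univariate variables and others of interest, which "were included in the subgroups to investigate the potential influences on the resolution of the thrombus", with continuous variables split at the median and a forest plot to follow.

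Under Study endpoints, "The primary endpoint of this study was the LV thrombus resolution rate at 12 weeks confirmed on contrast-enhanced echocardiography". A secondary endpoint is the "incidence of the composite of stroke, systemic embolism, myocardial infarction, and cardiovascular death during follow-up", which could also be the subject of a Cox model.

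Study procedures sets the timing. The sentence on repeat visits begins "Then, at 6 and 12 weeks, hematological parameters such as routine blood tests", and the imaging follows: "At the same time, contrast-enhanced echocardiography was also performed and thrombus size, anticoagulant use, and endpoint events were documented as well". The later contact has no scan: "Clinic or telephone follow-up visits were conducted at 6 months to collect events and anticoagulant use". On software, the plan says "All analyses were scheduled for completion with R version 3.5.1".

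**The concern.** If the hazard ratio is for resolution, the planned scans place each patient in one of three classes: resolved by week 6, resolved between weeks 6 and 12, or not resolved by week 12. The date of resolution is never observed. Cox regression would treat the scan as the moment of resolution, and almost all events would be tied at two times. A complementary log-log model with one intercept per interval is the grouped-time form of proportional hazards. It uses the same scans and its coefficient is still a log hazard ratio. On that argument Cox is the wrong choice: effects would be pulled towards 1, some power would be lost, and predictors of resolution could be missed or misjudged in the forest plot.

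**Working it through.** **Inputs.** From the documents: scans at weeks 6 and 12 only, two-sided 0.05, and median splits (hence two equal groups). Not in the documents, so assumed: constant resolution hazard; 35%, 50% or 65% of the reference group resolved by week 6; true hazard ratio (HR) 1 to 3; 15, 30 or 50 patients per group; Efron ties unless stated; punctual visits in steps 1 to 4. The plan states no figure to reproduce.

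**Step 1: what the grouped-time model targets.** Let p be the reference group's chance of resolving within an interval. The other group's chance is 1 − (1 − p)^HR. With p = 0.50 and HR 2 this is 1 − 0.5² = 0.75. The model recovers ln(1 − 0.75) / ln(1 − 0.50) = −1.386 / −0.693 = 2.00 in each interval.

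**Step 2: what Cox targets in large samples.** With r₁, r₀ at risk and d₁, d₀ resolving at a visit, the fitted HR θ makes the sum over both visits of

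d₁ − (d₁ + d₀) × average over u from 0 to 1 of θ(r₁ − u·d₁) / [θ(r₁ − u·d₁) + (r₀ − u·d₀)]

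equal to zero under Efron. Breslow sets u = 0. For p = 0.50 and HR 2, as fractions of each group:

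- Week 6: r₁ = r₀ = 1, d₁ = 0.75, d₀ = 0.50.
- Week 12: r₁ = 0.25, r₀ = 0.50, d₁ = 0.1875, d₀ = 0.25.

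Breslow is solved by θ = 1.50: at week 6, 0.75 − 1.25 × 1.5/2.5 = 0; at week 12, 0.1875 − 0.4375 × 0.375/0.875 = 0. Efron, by numerical integration, gives 1.89.

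| Resolved by week 6 | Efron, HR 1.5 | Efron, HR 2 | Efron, HR 3 | Breslow, HR 2 |
|---|---|---|---|---|
| 35% | 1.49 | 1.96 | 2.84 | 1.65 |
| 50% | 1.46 | 1.89 | 2.62 | 1.50 |
| 65% | 1.42 | 1.77 | 2.26 | 1.35 |

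**Step 3: total error in small samples.** True HR 2. Each cell gives the mean HR, then the root mean squared error (RMSE) of the log HR. Non-finite complementary log-log fits are dropped from both models. The first row has 2,000 replicates, the others 3,000.

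| Setting | Cox (Efron) | Complementary log-log |
|---|---|---|
| 30 vs 30, 50% by week 6 | 1.90; 0.283 | 2.06; 0.321 |
| 30 vs 30, 35% by week 6 | 1.97; 0.311 | 2.04; 0.329 |
| 15 vs 15, 50% by week 6 | 1.90; 0.388 | 2.14; 0.470 |

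In the first row the log-scale biases are ln(1.90/2) = −0.051 and ln(2.06/2) = +0.030. The squared Cox bias is 0.051² = 0.0026, about 3% of its mean squared error of 0.283² = 0.080. Variance dominates, and it is larger for the alternative (0.321² = 0.103 in all). Coverage was 95.6% for Cox and 94.5% for the alternative. Over 36 settings (three sizes, three week-6 rates, four HRs), Cox had the smaller RMSE in 33.

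**Step 4: error rate and power.** At 30 vs 30 with 50% resolved by week 6, a 4,000-replicate simulation gave type I error of 4.6% for Cox and 5.4% for the alternative. Power at HR 2 was 63% and 68%, so part of the gain comes from a slightly more liberal test.

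**Step 5: irregular scan dates.** With visit jitter (SD 0.7 week), no true effect and one group scanned 0, 1, 2, 3.5 or 7 days later, Cox on actual dates had type I error of 5%, 5%, 7%, 13% and 28%. Cox on nominal visits stayed at 4–6%.

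**The case for a change.** The best case for a change is that the plan leaves both the outcome and the tie method open, and the tie method matters. With Breslow ties a true HR of 2 is read as 1.35 to 1.65 in step 2. In a separate simulation with 100 patients, 40% of the reference group resolved by week 6 and 65% by week 12, power at HR 2 was 52% for Breslow, 82% for Efron and 84% for complementary log-log. A large effect with mostly early resolution also hurts Cox under Efron ties: at HR 3 with 65% resolved by week 6 its large-sample HR is 2.26, and small-sample coverage falls to 72–84%. The alternative costs a few lines of code and no new data.

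The arithmetic stands, but it does not carry the conclusion. Nothing in the documents points to Breslow ties. If they were used, the test would be conservative (0.6% rejection under no effect in the same simulation), so it would miss predictors and not invent them. The three settings where Cox had the larger RMSE all combine HR 3 with 65% early resolution, and there the alternative gave no finite estimate in roughly 11–53% of data sets. Small forest-plot subgroups are where such failures are likeliest. The alternative also shares one limit with Cox: a thrombus gone at week 6 counts as resolved even if it is back at week 12.

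It is also fair that the reader should know which event the HR describes. That is missing detail, and the next sentence of the plan already points to resolution.

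**Conclusion.** No change is needed. Resolution is interval-censored at two scans and the plan does not name the outcome of its Cox models, but a grouped-time model is not better overall at the sizes examined. With Efron ties and nominal visit times, Cox shrinks a true HR of 2 to about 1.8–2.0, keeps type I error near 5% and usually has the smaller total error. The alternative removes the large-sample bias and adds some power, at the price of higher variance, a slightly more liberal test and occasional non-finite subgroup estimates. That is a fair trade-off between two defensible models.

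The missing outcome name, event-time rule and tie method are details that an analyst can settle sensibly from the context. What is at stake is limited to predictor and subgroup hazard ratios in a study that its own title calls exploratory. The primary result, a 12-week rate with a 95% confidence interval, does not pass through the Cox model.

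The conclusion rests on assumed sample sizes, resolution rates, effect sizes and constant hazards, since the documents give none of these, and on Efron ties. It would weaken if Breslow ties were used, if effects were very large and resolution mostly early, or if actual scan dates differed between covariate groups by about half a week or more.
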